11.3.3.2 Serious Adverse Event Follow-up

The subject will be observed and monitored carefully until

- the event resolves, or
- the event/condition has stabilized (e.g., in the case of persistent impairment), or
- the event returns to baseline, if a baseline value is available.

Within 24 hours of receipt of new information, the updated follow-up SAE form, along with any supporting documentation (e.g., subject discharge summary or autopsy reports), should be faxed to Medpace Clinical Safety. All efforts must be taken to obtain follow-up information promptly.

Follow-up information may consist of:

- A hospital discharge summary for subjects who are hospitalized or hospitalized over a prolonged period due to the SAE. If possible, the discharge summary should be obtained when it becomes available.
- A copy of the autopsy report, if a death occurs and an autopsy is performed, should be obtained if possible when it becomes available.

Any SAEs that are ongoing at the end of treatment or early termination should be followed as described above. These data should be recorded on the source documents and submitted to the designee on a SAE report form. For ongoing SAEs, the investigator must submit follow-up SAE reports to the safety designee regarding the subject's subsequent course until the case is closed.

11.4 Pregnancy

Patients who become pregnant while on study will be taken off the study drug. In addition, pregnancies occurring up to 4 weeks after last dose should be reported to Medpace Safety. We will assist, as may be appropriate, in referral for

pregnancy-related medical attention, including high-risk obstetrical referral if requested, and will ask that the patient follow up with us and consent to share information as may be appropriate regarding the course and outcome of the pregnancy. We will ask for the patient to return for the regularly scheduled clinic visits so we can monitor them for any toxicity during the pregnancy. We will follow up with the patient after delivery in order to report any further AEs.

The investigator should report the pregnancy to Medpace Clinical Safety within 24 hours of being notified. Medpace Clinical Safety will then forward the Exposure In Utero form to the investigator for completion. If the outcome of the pregnancy meets the criteria for immediate classification as an SAE (i.e., postpartum complication, spontaneous abortion, stillbirth, neonatal death, or congenital anomaly), the investigator should follow the procedures for reporting an SAE.

11.5 Type and Duration of the Follow-up of Subjects after Adverse Events

Investigators will follow AEs until the event has resolved, the condition has stabilized, is well characterized, or referred to appropriate medical management, whichever comes first. Events and follow-up information occurring after the last visit should be recorded in the source documentation. Investigators are not obliged to solicit AEs after a subjects' final visit; however, if an investigator learns of an SAE that occurs within 4 weeks after the last dose, then an SAE report form should be submitted to Medpace Safety.

11.6 Pausing Rules for an Individual Subject

Pausing is the suspension of administration of study agent to a single subject until a decision is made whether or not to resume administration of the study agent.

The pausing criteria for a single subject in this study include any of the following:

- A subject experiences a Grade 3 laboratory event that is thought by the investigator to be possibly, probably or definitely related to study drug (see Appendix A)
- Any safety issue that the investigator determines should pause administration of a study agent to a single subject.

The PI will determine whether or not it is safe to resume administration of the study agent to the subject. A subject who does not resume CAMB will continue to be followed for safety.

11.7 Stopping Rules for an Individual Subject

A study subject will be discontinued from further study agent administration in the event of 1 or more of the following:

- Gastrointestinal toxicity (nausea/vomiting/diarrhea) that is interfering with the ability to perform regular every day activities.
- A subject experiences two Grade 3 events and/or one Grade 4 event that is possibly, probably, or definitely related to participation in the trial;
- SAE that is possibly, probably or definitely related to the study drug.
- Any laboratory abnormality, intercurrent illness, other medical condition or situation that occurs such that continued participation in the study would not be in the best interest of the subject.
- Any other events that the patient or investigators deems of clinical significance.

11.8 Halting Rules for the Protocol

The study will be halted (no new enrollments and no further administration of study drug) by the investigators and a report will be submitted to the IRB if 3 or more subjects experience one of the following in the 200 mg/day dosage level:

- · serum potassium values of 3 mmol/L or less
- serum creatine value that is above 1.2 mg/dL and is 50% or more above the baseline value

The IRB, the NIAID, the sponsor, the Food and Drug Administration (FDA), or other government agencies, as part of their duties to ensure that research subjects are protected, may discontinue the study at any time. Subsequent review of serious, unexpected and related AEs by the Medical Monitor, SMC, IRB, the sponsor, the FDA, and other regulatory authorities may also result in suspension of further trial interventions/administration of study agent at a site. The FDA, other regulatory authorities, and the study sponsor retain the authority to suspend additional enrollment and study agent administration for the entire study as applicable.

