- 400 mg/day. If on Day 14 the patient is determined to not be a clinical responder but the drug is well tolerated, then they will receive a single 200-mg dose in the morning. Blood, urine, saliva, stool (optional), and vaginal secretions (optional) will be collected over the next 24 hours for PK analysis. These patients will receive 400 mg/day (200 mg BID) for the next 14 days. They will have study visits on Days 17, 20, and 27. If on Day 27 they are determined to be a clinical responder and the drug is well tolerated, then they will receive a single 200-mg dose in the morning and blood, urine, saliva, stool (optional), and vaginal secretions (optional) will be collected over the next 24 hours for PK analysis. These patients will continue to receive 400 mg/day (200 mg BID) for the next 14 days. They will have a study visit on Days 34 and 41, and a final post treatment visit on Day 55.
- 800 mg/day. If on Day 27 the patient is determined to not be a clinical responder but the drug is well tolerated, then they will receive a single 400-mg dose in the morning. Blood, urine, saliva, stool (optional), and vaginal secretions (optional) will be collected over the next 24 hours for

PK analysis. These patients will receive 800 mg/day (400 mg BID) for the next 14 days. They will have study visits on Days 30, 33 and 40. If on Day 40 the patient is determined to not be a clinical responder, the study drug will be discontinued. At that point, follow-up procedures will be the same as an Early Termination Visit. If the patient is determined to be a clinical responder, the patient will continue to receive 800mg/day (400mg BID) for the next 14 days. They will have additional study visits on Days 47 and 54, and a final post treatment visit on Day 68.

 A long-term extension of up to 60 months of study treatment will be offered for patients who respond clinically to therapy and have no safety or tolerability concerns (See Section 6.6).

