3.2.2 Secondary Endpoints

- 1. Plasma, urine, and salivary single-dose and steady-state PK parameters and disposition of oral CAMB.
- 2. Dose linearity/proportionality of oral CAMB with titration.
- 3. Clinical Responder status after 28 days at the Target Dosage.
- 4. Clinical Responder status after 14 days at each dosage level.
- 5. Mycological response after treatment for 14 days and 28 day with the Target Dosage.
- 6. Mycological response after treatment with each dosage level for 14 days.
- 7. Rate of treatment-limiting toxicity.
- Rate of clinical relapse. Clinical relapse will be defined as a reoccurrence of clinical signs and symptoms after being sign and symptom free for 1 week.
- 9. Incidence of nephrotoxicity defined as an increase of more than 100% of

baseline serum creatinine.

- 10. Incidence of hypokalemia, defined as serum potassium ≤ 3 mmol/L during or within 3 weeks of completing treatment.
- 11. Incidence of AEs (see Section 11)
- 12. Clinical Responder status after 14 days of treatment at the Target Dosage per patient of a secondary, less severe candida infection. Clinical Responder will be defined as patients who achieve Complete Clinical Cure or Clinical Improvement.

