5.3.2 Dose Adjustments/Modifications/Delays

If the GFR falls below 60 mL/min/1.73m² or 30% lower than baseline then we will suspend treatment until GFR returns to baseline, in consultation with the safety monitoring committee.

For other toxicities thought to be the result of the study drug, including gastrointestinal symptoms, treatment will be suspended until the symptoms resolve. The investigator and patient will consider re-initiation on the basis of clinical findings and symptom severity.

5.3.3 **Duration of Therapy**

Subjects will take the study drug for 28 days at the clinically effective tolerated dosage (Target Dosage). However, if study drug is tolerated and the patient has clinical efficacy at two weeks, the extension phase of the protocol will be offered, in which the patient can continue the study drug for up to 60 months.

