6.6 Extension of Study Drug

Many of the patients expected to enroll into this study have underlying immunodeficiencies that predispose them to chronic mucocutaneous candidiasis, and recurrence is highly likely when the study drug is stopped. Therefore, study participants who are tolerating the study medication and are clinical responders, will be permitted to enroll in a study extension. The extension may be continued from the end of the period of medication administration (i.e. the end of the 2 week period of study medication at the dose that allows efficacy and tolerance of drug) or the participant may have a break of study medication before re-starting the extension period. If there is a break between the initial study drug use and the extension phase, the subjects will be offered alternative antifungals, such as

topical amphotericin swish and spit, to help control the oral pharyngeal candida infection. Breaks in study drug extension will be minimized as much as possible. Any break through infections may be treated by either the Principle Investigator or the subject's Primary Care Provider. In case of recurrence or worsening of the mucocutaneous candida infections while on the extension part of the study drug, despite excellent adherence, that requires new or additional antifungals, the Principal Investigator will stop the study drug.

Study drug will be continued at the minimum dose (100mg BID, 200mg BID, or 400mg BID) meeting clinical responder criteria with good tolerance. The investigator will have the ability to change daily dosage and frequency of study drug based on patient response and tolerability between the range of 200 mg to 800 mg per day.

Extension of study medication will be offered if the following criteria are met:

- Clinical responder status for oral, esophageal or vaginal disease at the end of the 2 week study point at the highest tolerated dose to which they respond (Day 14 for 200 mg, Day 27 for 400 mg, or Day 40 for 800 mg).
- The study participant does not have any of the laboratory criteria meeting the exclusion criteria
 - Alanine Transaminase (ALT), Aspartate Transaminase (AST) and Alkaline phosphatase (ALP) >2.5 times the upper limit of normal (ULN).
 - Total bilirubin level > 2.5 times the ULN
 - Serum creatinine level > 2 times the ULN
 - Absolute neutrophil count less than 500 cells/µL
 - Potassium level <3.5 mmol/L
- Good tolerance of study drug

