 - No gastrointestinal toxicity (nausea/vomiting/diarrhea) that is interfering with the ability to perform regular every day activities.
 - Less than two Grade 3 events and/or one Grade 4 event that are possibly, probably, or definitely related to participation in the trial;
 - No SAEs that are possibly, probably or definitely related to the study drug.
- No laboratory abnormalities, intercurrent illness, other medical condition or situation that occurs such that continued participation in the study would not be in the best interest of the subject.

Study medication will be allowed to continue for up to 60 months with the following monitoring:

- Bi-weekly safety laboratories (or more frequently as per PI discretion)
 including CBC/diff, chemistry panels (hepatic, mineral and acute). These
 can be performed at the NIH clinical center or at the home laboratory. (+/4 days)
- Bi-weekly visits to the NIH clinical center (+/- 3 days) for the first 1 month and then the visits can be extended to every 12 weeks (+/- 7 days) unless clinically indicated to be more frequent. At these visits the following study procedures will be performed:
 - Clinical assessment and physical exam
 - Assessment of AEs and concomitant medications
 - Blood draw including CBC/diff, chemistry panels (hepatic, mineral and acute), and urinalysis.
 - Pregnancy testing (except week 2 NIH visit after start of extension phase)
 - Serum and PBMCs may be collected for storage
 - Urine, plasma, stool, saliva and vaginal secretions may be collected and stored
 - Microbiology (fungal culture of affected sites)
 - OMC Picture of affected areas every 8 weeks

If study participants are only seen every 12 weeks, they will be contacted by phone or NIH-approved video conference platform at the 2-week interim point to assess for AEs, concomitant medications, and drug compliance. The laboratory testing can be performed by a local laboratory and a copy of the results should be sent to the investigator.

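### The numeric halting rule counts low potassium and raised creatinine only at 200 mg/day, so potassium of 2.5–3.0 mmol/L at higher doses reaches the safety committee only through investigator judgment

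*Combined protocol and SAP*

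**What the plan says.** Section 11.8 stops new enrollment and all dosing "if 3 or more subjects experience one of the following in the 200 mg/day dosage level". The events are serum potassium of 3 mmol/L or less, and serum creatinine (printed as creatine) above 1.2 mg/dL and at least 50% over baseline. Neither has to be judged drug-related. No section gives a count for the same events at 400 or 800 mg/day.

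Those doses are a planned part of the trial. Under Section 3.1, non-responders who tolerate the drug move to 400 mg/day at Day 14 and to 800 mg/day at Day 27: "These patients will receive 800 mg/day (400 mg BID) for the next 14 days", with 14 more days for responders. In the extension (Section 6.6), the investigator may adjust the dose for response and "tolerability between the range of 200 mg to 800 mg per day", for up to 60 months.

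Other provisions apply at every dose:

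- **Section 5.3.2.** If GFR falls below 60 mL/min/1.73m² or 30% below baseline, the team will "suspend treatment until GFR returns to baseline, in consultation with the safety monitoring committee". Other toxicities thought to be drug-related also suspend treatment, with no grade limit and no mention of the SMC.
- **Sections 11.6 and 11.7.** A related Grade 3 laboratory event pauses the patient. Two related Grade 3 events or one related Grade 4 event stop the patient. Both sections also allow action on investigator judgment.
- **Section 11.10.1.** The SMC is told at once when a pausing, stopping or halting rule is met, and makes a study-level recommendation. It sets its own meetings after the first scheduled review.
- **Section 11.8, second paragraph.** The IRB, NIAID, sponsor or FDA may discontinue the study at any time.
- **Section 6.6.** "Potassium level <3.5 mmol/L" bars entry to the extension, and chemistry is then checked every two weeks.
- **Section 3.2.2.** Endpoint 9 is "Incidence of nephrotoxicity defined as an increase of more than 100% of" baseline creatinine. Endpoint 10 is "Incidence of hypokalemia, defined as serum potassium" of 3 mmol/L or less.

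**The concern.** The plan treats these two laboratory findings as grounds for stopping the whole trial at the lowest dose. The same findings at two to four times that dose count toward nothing at study level. Section 5.6 recognizes hypokalemia as an amphotericin effect, and Section 1.2 says that the nephrotoxicity of parenteral amphotericin worsens with longer courses. The numeric rule therefore goes silent where dose is highest and exposure longest.

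What is at stake is recognition of a pattern. Several patients could reach potassium of 3 mmol/L or less at 400 or 800 mg/day without any prespecified point at which someone independent of the trial team asks whether the events belong together. Endpoint 10 would tally them, but only in the descriptive analysis.

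**Working it through.** **1. The plan's own figure.** No operating characteristic is given for the halting rule. The only computed figure is the efficacy rule in Section 13.2 (3 or more of 16). With P(X ≥ 3) = 1 − Σ C(16,k) p^k (1−p)^(16−k) for k = 0 to 2, the result is 0.0429 at p = 0.05 and 0.803 at p = 0.25, matching the stated 0.043 and 0.80. It does not bear on this point. The same formula describes a 3-subject halt among 16 patients at 200 mg/day. At assumed event rates of 5%, 10%, 20% and 30%, it triggers with probability 0.043, 0.211, 0.648 and 0.901. Events above 200 mg/day add nothing to that count.

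**2. Main-phase dosing outside the count** (Section 3.1 schedule; higher dosing starts with the Day 14 dose):

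- 400 mg/day responder: Days 14–41 = 41 − 14 + 1 = 28 of 41 days (68%).
- 800 mg/day responder: Days 14–54 = 54 − 14 + 1 = 41 of 54 days (76%).

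These are the longest courses. They measure exposure, not risk.

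**3. Potassium**, setting Appendix A against Sections 11.6–11.8:

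| Potassium (mmol/L) | Grade | At 200 mg/day | Above 200 mg/day |
|---|---|---|---|
| 3.0 | 1 | counts toward halt | no graded rule; judgment only |
| 2.5–2.9 | 2 | counts toward halt | no graded rule; judgment only |
| 2.0–2.4 | 3 | counts toward halt | pause if thought related; SMC told |
| below 2.0 | 4 | counts toward halt | stop if related; SMC told |

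A need for intensive replacement or hospitalization also makes the event Grade 3. In the first two rows, action above 200 mg/day requires the investigator to attribute the event to the drug (5.3.2) or to choose to pause or stop (11.6, 11.7).

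**4. Creatinine.** If GFR varies inversely with creatinine (an assumption), a 50% rise gives a GFR ratio of 1/1.5 = 0.667, a 33% fall. That passes the 30% limit in Section 5.3.2. Each creatinine event of the 11.8 kind would then suspend treatment in consultation with the SMC, at any dose.

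**5. Timing of SMC review.** After initiation, the one fixed review comes when 3 subjects have had about 3 weeks of drug. On the nominal schedule that is at most about one week into 400 mg/day, and 800 mg/day starts at Day 27. No review is guaranteed to follow exposure at 800 mg/day.

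**6. Form of an added count.** A separate count of 3 at each level could leave 2 + 2 = 4 affected patients without a trigger. A pooled count of 3 leaves at most 2. The number dosed above 200 mg/day and the event rates are not in the documents, so the chance that a pooled count triggers is shown over assumed ranges:

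| Patients above 200 mg/day | 10% | 20% | 30% | 50% |
|---|---|---|---|---|
| 4 | 0.004 | 0.027 | 0.084 | 0.312 |
| 8 | 0.038 | 0.203 | 0.448 | 0.855 |
| 12 | 0.111 | 0.442 | 0.747 | 0.981 |
| 16 | 0.211 | 0.648 | 0.901 | 0.998 |

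Under the current text every cell is zero.

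**The case against.** The restriction to 200 mg/day may well be deliberate. Everyone starts there, and only non-responders who tolerate the drug go higher. Repeated toxicity at the lowest dose leaves no lower protocol dose, so halting fits. At a higher dose the patient can be stopped or, in the extension, given less. Extending the full halt upward would take drug from responders at 200 mg/day. This stands, and is why the remedy should not be a second halt.

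It can also be argued that the potassium gap is already closed. A value thought drug-related leads to suspension under 5.3.2; a suspension is in substance a pause under 11.6; and a pause brings immediate SMC notice under 11.10.1, from the first patient. Where the investigator attributes the event, this largely stands. It leaves two weaknesses. Section 5.3.2 ties suspension to resolution of symptoms, which fits symptomless hypokalemia poorly. And the chain starts only with attribution or judgment. The Grade 3 pausing rule needs attribution too, so the telling contrast is with the 11.8 count, which needs none.

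The creatinine side of the objection succeeds for single cases, on the inverse-GFR assumption: the SMC is consulted from the first one.

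The practical effect is also small. Enrollment is closed, and Section 1.1.1 places participants in the extension. Section 14.1.1 mentions reconsent from the final enrolled participant, which could mean the last one enrolled or the only one remaining. Section 1.1.3 reports 37 subjects in another study, with a different concentration, who tolerated up to 1.5 g daily without serious or unexpected adverse events. All of this stands and limits the severity.

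**Conclusion.** The point holds as a cheap improvement, severity CONSIDER. The attribution-free count of 3 stops at the lowest dose, and no number of the same events above it triggers study-level action. The substantive gap is potassium of 2.5–3.0 mmol/L at 400 or 800 mg/day, where suspension and SMC notice rest on the investigator.

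Two stronger readings are tempting and are not supported:

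- A reader might infer that the higher doses have no study-level oversight. They do: SMC notice of pauses and stops, an SMC that sets its own meetings and recommends on the whole study, and discretionary authority to discontinue. What is missing is a numeric trigger.
- A reader might infer from endpoint 9 that creatinine rises of 50–100% above 200 mg/day are lost. Section 13.3.2 summarizes creatinine and its change from baseline, endpoint 11 covers adverse events, and 5.3.2 probably catches such rises one by one.

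The finding rests on the text. The creatinine conclusion depends on the inverse-GFR assumption. The documents give neither an event rate for repeated dosing in this population nor the number still dosed above 200 mg/day, so no probability of harm is claimed. With enrollment closed, the effect falls mainly on extension dosing.

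**What to change.** Keep the 200 mg/day halt and add to Section 11.8:

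> If 3 or more subjects in total, counted from study start, have potassium of 3 mmol/L or less or meet the creatinine criterion while dosed above 200 mg/day (400 and 800 mg/day pooled, main phase or extension), further dose escalation is held and the SMC is notified immediately to review the cases and recommend continuation, modification or termination. Patients already responding continue under the individual rules.

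Counting from study start keeps the trigger reachable if fewer than 3 patients are still dosed above 200 mg/day. Holding escalation still has meaning because Section 6.6 lets the investigator raise extension doses to 800 mg/day.

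The cost is amendment wording; the laboratory results are already collected. The downside is an occasional extra SMC review, or a short hold on escalation, for events that prove unrelated, such as hypokalemia potentiated by corticosteroids (Section 5.6). If the sponsor prefers the present rule, a sentence explaining why the count stops at the lowest dose would help.
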